15.3 Sample size

Up to 60 healthy female subjects will be included in 2cohorts of 30 subjects respectively.

15.4 Studied criteria

15.4.1 Characteristics of included subjects

- **Subject disposition**
Subject disposition will be presented for the RAN set and will include the number enrolled, the number in each subject population for analysis (RAN, SAF, IG and PP), the number who withdrew prior to completing the study and primary reason for withdrawal (if applicable).
- **Subject demographic characteristics**
For demography, continuous variables (for example: age, height, weight, BMI) and qualitative variables (for example: ethnic origin) will be summarized using descriptive statistics on the SAF population. Demographic characteristics will be also presented for other study populations (IG and/or PP) if they are different from SAF.
- **Medical history events**
Medical and surgical history events will be coded using MedDRA (latest version) and will be summarized by System Organ Class (SOC) and Preferred Term (PT). Subjects will contribute only once per SOC and PT. In case of few relevant history events (≤ 5 per study part for example), only a listing will be provided according to treatment/dose group and subject.
- **Physical examination**
Abnormal physical findings at screening period or at V2 pre-dose (study baseline) will be listed by treatment/dose group, subject and visit.

- **Pregnancy test**
Serum pregnancy test will be performed at screening and post-study medical visit and urine pregnancy test will be performed prior to each administered dose (primary and booster doses at Visit 2 and Visit 6 respectively). A listing of positive results will be presented by treatment/dose group, subject and visit.
- **Previous medications**
Previous medications will be listed and will be presented by treatment/dose group and subject.
- **Concomitant medication**
Concomitant treatments will be listed by treatment/dose group.

15.4.2 Primary endpoint

The primary objective is to evaluate the safety and tolerability of the GBS-NN/NN2 vaccine for 12 weeks after the first dose of vaccine.

All the subjects included in the SAF set (including the withdrawal and dropout subjects) will be evaluated for safety analysis.

The following endpoints will be evaluated:

- **Local and systemic reactogenicity**

Assessment results will be described according to treatment/dose group and visit.

- **Adverse events**

Adverse events will be coded according to the Medical Dictionary for Regulatory Activity (MedDRA, latest version). They will be classified into pre-defined standard categories according to chronological criteria:

Treatment Emergent Adverse Events (TEAEs): AEs which occur for the first time after the first administration or present before and worsened during vaccine exposure.

Non-Treatment Emergent Adverse Events (NTEAEs): AEs which occur before the first study vaccine administration (also called “pre-dose event”).

TEAEs will be described by relation to study vaccine (for example: related or unrelated) and maximum intensity (for example: mild / moderate / severe) according to treatment/dose group. Descriptive statistics will be characterised by number of TEAEs, number and percentage of subjects with at least one TEAE (based on SAF). In case of few TEAEs (≤ 5 per study part for example), only a listing will be performed.

If descriptive statistics are performed, vaccine relation of TEAEs (*i.e.* related or not related to study vaccine) will be summarized by MedDRA codes (SOC and PT) and treatment/dose group.

Two distinct listings of TEAEs and NTEAEs will be presented by treatment/dose group, subject and MedDRA codes in order to provide more information about adverse events (example: description, duration, time since last administration if

applicable, seriousness, relation to study vaccine, any actions taken as concomitant medication or hospitalization).

- **Laboratory tests**

Biochemistry and haematology tests will be performed at V1 (screening), V2, V4, V5, V8, post-study medical V10 and V11.

Parameter values, position according to laboratory ranges (if available) and investigator assessment will be listed according to visit for each treatment/dose group. In order to assess study evolution of parameters after vaccination, parameter values changes from pre- to post-dose visits (baseline to pre second dose Day 29 (effect of first dose) and baseline and pre second dose to 28 days after second dose (Day 57) then base line to Day 85). will be calculated. Emergent values (for parameters with available laboratory ranges; values not within this range) with their corresponding position according to ranges will be listed by treatment/dose group and subject.

- **Urinalysis**

Urinalysis will be performed at V1 (screening), V4, V8 and post-study medical visit V10.

Parameter values (quantitative or binary results, *i.e.* positive/negative), position according to laboratory ranges (if available) and investigator assessment will be listed according to visit for each treatment/dose group. In order to assess study evolution of continuous parameters after vaccination, parameter values changes from screening to post-study medical visit will be performed. Emergent values (for parameters with available laboratory ranges or with binary results) will be listed by treatment/dose group and subject.

- **Vital signs**

Vitals signs will be characterised by heart rate, blood pressure, oral temperature and respiratory rate. Vital signs will be assessed at V1 (screening), V2 (pre-dose, T2h and T4h post-dose), V3, V4, V5, V6 (pre-dose and T2h post-dose), V7, V8, and post-study medical V10 and V11.

Parameter values, position according to reference ranges (if available) and investigator assessment will be described according to visit and assessment time for each treatment/dose group. In order to assess study evolution of parameters after vaccination, parameter values changes from pre-dose to post-dose assessments will be performed. Emergent values (for parameters with available reference ranges; values not within this range) with their corresponding position according to reference ranges will be listed by treatment/dose group and subject.

- **12-lead ECG parameters**

ECGs will be assessed at V1 (screening).

Parameter values, position according to reference ranges and investigator assessment (if available) will be described according to visit for each treatment/dose group. Emergent values (for parameters with available reference ranges; values not

within this range) with their corresponding position according to reference ranges will be listed by treatment/dose group and subject.

- **Physical examination**

Abnormal physical examinations recorded at post-study medical visit VI0 andVII will be listed according to treatment/dose group and subject.

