6.3 Risk/Benefit Assessment

Antibodies against the full-length Rib, AlphaC, Alp1, Alp2 and Alp3 proteins, from which the GBS-NN and GBS-NN2 are derived to make up the vaccine antigens, naturally occur in women exposed to GBS, and such antibodies are efficiently transferred to the unborn child *in-utero*. Many adults and new-born infants have, therefore, already been naturally exposed to the proteins from which the antigen is derived and to antibodies against these proteins, and no side effects have been attributed as a consequence of such exposure in humans.

[REDACTED]

[REDACTED]. The maximum human dose will be 50 µg, which if administered to a 60 kg woman would equate to 0.83 µg/kg giving a safety margin of at least 60-fold.

The planned excipients in the vaccine formulation are also all well-known from other vaccines, and no novel or non-tested components are used. The proteins in the vaccine are adsorbed with a known adjuvant, Alhydrogel®, (0.5 mg of Al³⁺ per dose), corresponding to the dose used in many other commercial vaccines.

This is a new investigational product; therefore, there are currently no expected AEs related to the product. However, following injection of GBS-NN alone, approximately 30% of the subjects in the study experienced mild pain. Pain post-injection that is worse than mild would be considered to be unexpected. It is not anticipated that adding the two additional antigenic proteins, to GBS-NN, bound to Alum will significantly alter the safety profile. The Investigator is responsible for reporting adverse events (AEs) that occur during the course of the study. Serious adverse reactions that are deemed to be related to the investigational product in the proposed study will be reported as suspected unexpected serious adverse events (SUSAR).

GBS-NN/NN2, like other protein-based vaccines, may theoretically be associated with a transient febrile reaction (body temperature greater than 38.0°C but not greater than 38.7°C) following vaccination. Immune complex-mediated reactions are unlikely given the recombinant nature of GBS-NN/NN2, however, it is still possible that hypersensitivity may occur.

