10.4 IMP Administration

Administration will be by intramuscular injection into the deltoid muscle of one of the subject's arms. For the second dose the subjects opposite arm should be used in the event that the first injection site has not healed.

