15.1 Statistical method description

15.1.1 General information

Demographic, baseline characteristics and data recorded during the study will be summarized using descriptive statistics by treatment (placebo or vaccine) and dose group, unless otherwise specified.

Individual data will be presented as a data listing, sorted by treatment and administered dose level.

For parameters with evaluation before vaccination and in case of re-checked value(s), only the last observation prior to dosing will be used in descriptive and inferential statistics and derivations of other parameter values. After vaccination, only values of scheduled assessments (planned in the protocol) will be used.

For laboratory/clinical parameters for which laboratory/reference ranges will be available, position of parameter values according to ranges will be flagged with the following rule:

- "L" for values lower than laboratory/reference ranges;
- "H" for values higher than laboratory/reference ranges.

In addition, parameter values can be assessed by investigator and flagged as follows in order to determine clinical relevance:

- Normal;
- Abnormal and NCS (Not clinically Significant);
- Abnormal and CS (Clinically Significant).

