15.1.2 Descriptive statistics

Descriptive statistics for quantitative parameters will be provided using number of observations (N), Geometric mean, 95% confidence intervals, standard deviation (SD), minimum, median and maximum. Descriptive statistics for qualitative parameters will be provided using absolute frequencies (n) and relative frequencies (%). For immunological endpoints (IgG concentration and fold increase) geometric means with 95% confidence intervals for the geometric mean will additionally be presented.

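### Section 15.4.2 specifies no summary of women with any local reaction, or their worst grade, after dose 1 and after dose 2; by-visit percentages and whole-period TEAE counts cannot supply it

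*Combined protocol and SAP*

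**What the plan says.** Under local and systemic reactogenicity, section 15.4.2 states: "Assessment results will be described according to treatment/dose group and visit". Section 15.1.1 fixes the grouping: data are "summarized using descriptive statistics by treatment (placebo or vaccine) and dose group, unless otherwise specified". That separates placebo, 25 µg and 50 µg, but not the two injections. Section 15.1.2 fixes the format: "Descriptive statistics for qualitative parameters will be provided using absolute frequencies (n) and relative frequencies". No interval is named for proportions outside the immunological endpoints.

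For adverse events, section 15.4.2 defines TEAEs as "AEs which occur for the first time after the first administration or present before and worsened during vaccine exposure" and summarises the "number and percentage of subjects with at least one TEAE (based on SAF"). The window is not divided at the second dose. A listing is to carry, among other items, "description, duration, time since last administration if" applicable.

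The schedule in section 18 places injection site assessments at every visit from Visit 2 to Visit 10. Section 12.2 describes two at Visit 6: one with the checks before the second dose, and one in the examination before discharge.

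**The concern.** A percentage at a visit is a point prevalence. It says how many women had a finding when looked at, not how many ever had one after that injection, nor the worst grade each reached. For a two-dose vaccine those per-dose figures are a natural description of tolerability.

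Three features make the specified summaries harder to read by dose:

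- **Visit 6.** A single row for this visit would mix the late aftermath of dose 1 with the first hours after dose 2. Section 15.4.2 describes vital signs by visit and assessment time, but reactogenicity by visit alone.
- **Denominators after dose 2.** Women who meet an individual stopping criterion (section 12.6), or become pregnant between doses (section 9.5), receive no second injection but stay in follow-up. They could be counted in percentages at Visits 7 to 10.
- **Attribution.** Section 10.4 allows for a first site still unhealed at the second dose: "For the second dose the subjects opposite arm should be used in the event that the first injection site has not healed". No text in section 15.4.2 says how a finding seen after Visit 6 is assigned to a dose.

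The plan does separate the doses elsewhere. Laboratory changes to Day 29 are labelled as the effect of the first dose (section 15.4.2), and antibody thresholds at Days 29 and 85 are meant to show the response to each dose (section 15.4.3). The primary endpoint has no equivalent.

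**Working it through.** The plan states no figure to reproduce: section 15.3 gives only the number of subjects. The check is whether the specified summaries determine a per-dose share. Group size is 24 vaccinees and 6 placebo per cohort (synopsis, Study Design). All reaction counts below are assumptions for illustration.

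**1. From by-visit counts to women who ever reacted.** If c₁, …, c_k women of n have a reaction at k looks, the number ever reacting at those looks, U, satisfies

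max(cᵢ) ≤ U ≤ min(n, Σcᵢ).

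- Counts 7, 5, 2, 1 of 24 at Visit 2 post-dose, Visit 3, Visit 4 and Visit 5: lower bound 7/24 = 29.2%; upper bound 7+5+2+1 = 15, so 15/24 = 62.5%.
- Counts 4, 4, 4 of 24 at three looks: 4/24 = 16.7% to 12/24 = 50%, while every by-visit figure reads 16.7%.

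The upper ends require no overlap between visits. They are limits, not expectations.

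**2. From the whole-period count to the two doses.** If W women ever have the event, and d₁ and d₂ have it after each dose,

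max(d₁, d₂) ≤ W ≤ d₁ + d₂.

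With W = 12 of 24, the pairs (12, 0), (0, 12), (6, 6), (4, 12) and (12, 12) all fit. The whole-period figure does not determine the split.

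**3. Denominator after dose 2.** If one of 24 women is not given dose 2 and 7 react to it, the share is 7/23 = 30.4% of those dosed and 7/24 = 29.2% of all. This is a small effect per woman, but a severe reaction to dose 1 is itself one of the reasons for not receiving dose 2.

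**4. Looks after each dose** (sections 12.2 and 18, nominal days):

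| Look | After dose 1 | After dose 2 |
|---|---|---|
| Before discharge | Visit 2 | Visit 6 post-dose |
| 24 hours | Visit 3 | Visit 7 |
| 7 days | Visit 4 | none |
| 14 days | Visit 5 | Visit 8 |
| 28 days | Visit 6 pre-dose | Visit 9 |
| 56 days | not applicable | Visit 10 |

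Four looks are shared. The full windows are Day 1 to Day 29 (28 days) and Day 29 to Day 85 (56 days), so worst grades over the full windows are not like for like.

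**5. Precision.** Exact (Clopper–Pearson) limits are the 0.025 quantile of Beta(x, n−x+1) and the 0.975 quantile of Beta(x+1, n−x).

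- 7/24 = 29.2%: 12.6% to 51.1%.
- 0/24: upper limit 1 − 0.025^(1/24) = 14.2%.
- 2/12 (placebo pooled over cohorts) = 16.7%: 2.1% to 48.4%.

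**The case against.** The strongest reply is that the doses can already be compared. Visits 3 and 7 are each 24 hours after an injection, with the same window, and Visits 5 and 8 are each 14 days after one. The n and % at those visits give matched figures. This stands. A reader might infer that the trial cannot say whether the second dose is worse tolerated; the documents do not support that. What is absent is the any-time, worst-grade figure.

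A reader might also infer that the trial will report a figure below its own benchmark, section 6.3's statement that with GBS-NN alone "approximately 30% of the subjects in the study experienced mild pain". That does not follow either. The benchmark is not split by dose, and the TEAE summary is a per-woman incidence over the whole period that can be set beside it. How many Appendix I findings reach the TEAE tables is less clear. Section 14.1 defines an AE broadly, whereas section 14.6 makes abnormal assessment findings AEs only if clinically significant or leading to intervention.

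Other replies have weight. Section 15 presents only important features and leaves details to an SAP, and no separate SAP text is in the document reviewed, so the gap is in the protocol as written. Individual listings and the time since last administration make the split recoverable without new TEAE data. Sections 12.2 and 18 speak of injection sites in the plural, and the eCRF is not supplied, so a missing arm or dose field cannot be asserted. Finally, no stated decision uses a per-dose rate: escalation rests on data through Visit 4, and the percentage stopping rules in section 12.7 count subjects in a cohort.

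**Conclusion.** The point holds as a gap in the specified summaries, not in the data. As written, section 15.4.2 yields prevalence at each visit and a whole-period TEAE incidence. Neither gives the share of women with any local reaction, or their worst grade, after each dose. In the illustration, by-visit figures peaking at 29.2% fit a true post-dose-1 share anywhere up to 62.5%; the actual gap depends on how far the same women react at successive visits, which is unknown in advance. The mixing at Visit 6 follows from a summary by visit alone. The denominator and attribution problems are possibilities that the text leaves open, not certainties.

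That per-dose rates matter for tolerability is a judgement, since the documents set no per-dose criterion. It is supported by the primary objective and by the plan's own separation of doses for laboratory and antibody data. The change is worth making because it is inexpensive and serves the primary objective. It alters neither the sample size nor any clinical procedure.

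**What to change.** In section 15.4.2 and the SAP:

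- Add, for each treatment/dose group and reaction type, each woman's worst Appendix I grade after dose 1 (Visit 2 post-dose to Visit 6 pre-dose) and after dose 2 (Visit 6 post-dose to Visit 10). For pain use the highest rating; for itching, present or absent, as the appendix records them. Give n, % of women who received that dose, and exact 95% CI.
- Report the Visit 6 pre-dose and post-dose assessments separately, and attribute each finding to an injection site and dose.
- Compare dose 1 with dose 2 only on the shared looks: before discharge, 24 hours, 14 days and 28 days. Do not compare the full-window worst grades, because the windows and visit schedules differ.
- Tabulate TEAEs by onset before or after dose 2, as well as overall.

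Keep the by-visit summary for the time course. The cost is SAP wording, a few extra tables and, only if the eCRF does not already record it, an arm/dose field.

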12.2 Treatment Period and Post-Study Period

Subjects will be administered the primary dose of the appropriate dose of GBS-NN/NN2 or placebo according to the cohort and dosing schedule described in section 10.1 at Visit 2 and a second dose will be administered at Visit 6. All cohorts will incorporate sentinel dosing of 2 subjects in each cohort for the primary dose only: 1 on active treatment and 1 on placebo. No further subjects in that cohort will be dosed until 24 hours after dosing the second subject, provided that there are no serious or unexplained safety issues as determined by the Investigator.

The decision to proceed with administration of the primary dose in the subsequent cohort will be made as described in Section 12.5.

The following assessments will be carried out at these visits:

Visit 2

A general medical review, vital signs, urine pregnancy test, urine drugs of abuse test and alcohol urine test will be performed to re-confirm eligibility. Eligible subjects will then be randomised to receive the appropriate treatment as per the randomisation list for the cohort. A pharmacodynamic blood sample will be taken to measure pre-existing antibody levels and to obtain Peripheral Blood Mononuclear Cells (PBMCs) to assess cellular responses, prior to

dosing. Blood sample for haematology and serum biochemistry will be taken. Vital signs will be recorded at pre-dose (within 60 minutes of dosing), 2 (± 0.25) and 4 (± 0.25) hours post-dose. A general medical examination (including an assessment of the injection site) will be performed prior to discharge to ensure the subject is fit for discharge. At discharge subjects will be provided with oral temperature kit and instructed to record a temperature if they feel unwell in the seven days post dose.

Visit 3

Visit 3 will be performed 24 hours (± 2 hours) after administration of the primary dose and an assessment of the injection site will be performed, vital signs will be recorded and AEs and concomitant medications will be reviewed.

Visit 4

Visit 4 will be performed 1 week (± 1 day) after administration of the primary dose. An assessment of the injection site will be performed, vital signs will be recorded, safety blood samples for haematology and biochemistry will be collected, urinalysis will be performed and AEs and concomitant medications will be reviewed.

Visit 5

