Visit 5 will be performed 2 weeks (± 2 days) after administration of the primary dose. This visit will review of AEs and concomitant medications. An assessment of the injection site will be performed, vital signs will be recorded, safety blood samples for haematology and biochemistry will be collected and a pharmacodynamic blood sample will be taken to measure the antibody response.

Visit 6

Visit 6 will be performed 4 weeks (± 3 days) after Visit 2. An assessment of the injection site, AEs and concomitant medications review, urine pregnancy test, and a pharmacodynamic blood sample will be taken to measure the antibody response prior to administering the second dose. Vital signs will be recorded pre-dose and at 2 (± 0.25) and 4 (± 0.25) hours post-dose. A brief medical examination (including an assessment of the injection sites) will be performed prior to discharge to ensure the subject is fit for discharge. At discharge subjects will be provided with oral temperature kit and instructed to record a temperature if they feel unwell in the 7 days post dose.

Visit 7

Visit 7 will be performed 24 hours (± 2 hours) after administration of the booster dose and an assessment of the injection sites will be performed, vital signs will be recorded and AEs and concomitant medications will be reviewed.

Visit 8

Visit 8 will be performed 2 weeks (± 2 days) following Visit 6 and the following assessments will be performed: an assessment of the injection sites, vital signs will be recorded, safety blood samples for haematology and biochemistry will be collected, urinalysis will be performed, a pharmacodynamic blood sample will be taken to measure antibody response and to obtain PBMCs to assess cellular responses, and AEs and concomitant medications will be reviewed.

Visit 9

Visit 9 will be performed 8 weeks (± 2 days) following the first study vaccine administration and the following assessments will be performed: an assessment of the injection site and a pharmacodynamic blood sample will be taken to measure antibody response and AEs and concomitant medications will be reviewed.

Visit 10

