13. PHARMACODYNAMIC ANALYSIS AND ASSESSMENTS

13.1 Pharmacodynamic blood sample – antibody response

Each blood sample will be approximately 20 mL in volume, to yield approximately 10 mL of sera. The sera will be divided into aliquots, as described in the laboratory manual. Seven samples will be collected during the study which represents approximately 140 mL of blood.

The total blood volume taken over the study will be approximately 300 mL, which represents seven of approximately 20 mL pharmacodynamic samples, two of approximately 40 mL PBMC's and seven of approximately 9 mL clinical laboratory blood samples.

Pharmacodynamic samples will be collected at the following timepoints; Day 1, Day 15, Day 29, Day 43, Day 57, Day 85 and Day 210

Detailed processing instructions will be included in a separate lab manual.

[REDACTED]

Serum samples for PD antibody response analysis will be performed at [REDACTED] at [REDACTED] and [REDACTED]

Serum samples will be assayed in a validated ELISA to measure the concentrations of IgG specific for GBS-NN and GBS-NN2. Raw data from the assay will be inspected by the QC/QA scientists at the analytical lab to identify any samples which give unexpected results based on the normal kinetics of IgG induction following vaccination. Such unexpected values may indicate a problem with sample identification or with the assay performance. Potentially anomalous results will be discussed with the sponsor, without revealing the identity of the subjects, and if necessary samples will be re-analysed and corrected if the result fits with expectation. If the re-analysis returns essentially the same result a decision will be taken on whether to exclude the samples from the IG population analysis. Prior to formal statistical analysis of the results a standard test for outliers (e.g. the ROUT function in Graphpad Prism or equivalent) will be performed and any data points identified will be excluded from the analysis. In parallel the analysis will be performed on all data points including outliers to reveal the magnitude of the effect of excluding them.

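### Section 15.4.2 plans laboratory changes to Day 29 and Day 57, visits with no scheduled safety bloods; as written, only the change from baseline to Day 85 can be computed

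*Combined protocol and SAP*

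**What the plan says.** The laboratory item of section 15.4.2 makes two statements that do not fit together.

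- **When bloods are drawn:** "Biochemistry and haematology tests will be performed at V1 (screening), V2, V4, V5, V8, post-study medical V10 and V11".
- **Which changes are derived:** "baseline to pre second dose Day 29 (effect of first dose) and baseline and pre second dose to 28 days after second dose", the latter given as Day 57, followed by baseline to Day 85. The stated purpose is to follow the parameters after vaccination.

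Day 29 is Visit 6 and Day 57 is Visit 9. Section 12.2 describes Visit 6 as "An assessment of the injection site, AEs and concomitant medications review, urine pregnancy test, and a pharmacodynamic blood sample will be taken", before the second dose. It describes Visit 9 as "an assessment of the injection site and a pharmacodynamic blood sample will be taken to measure antibody response and AEs and concomitant medications" being reviewed. Neither entry contains haematology or biochemistry. Section 13.1 counts "seven of approximately 9 mL clinical laboratory blood samples" per subject, and the safety laboratory row of Table I is blank at Visits 6 and 9.

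Three general rules bear on the point.

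- For values before vaccination, section 15.1.1 says that "in case of re-checked value(s), only the last observation prior to dosing will be used in descriptive and inferential statistics". The sentence opens by covering parameters evaluated before vaccination, so it is not confined to repeats.
- After vaccination, 15.1.1 admits only scheduled values.
- Section 15.2 does not replace missing data unless otherwise specified.

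For Visit 2, section 12.2 places the pharmacodynamic sample before dosing. Of the safety sample it says only "Blood sample for haematology and serum biochemistry will be taken".

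**The concern.** Safety and tolerability up to Day 85 is the primary objective, and these are the only laboratory changes that the protocol specifies. One is labelled as the effect of the first dose. Another, from before the second dose to 28 days after it, is the only one that would isolate the second dose. If the time points carry no samples, neither can be produced as described. What remains is a change to Day 85, nominally 84 days after dose 1 (85 − 1) and 56 days after dose 2 (85 − 29).

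Meanwhile, draws that do follow each dose have no specified change: Days 8, 15 and 43 as written, or Days 8 and 43 if Day 15 is taken as the value before dose 2. The SAP must then either repeat a derivation that cannot be run or depart from the protocol.

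**Working it through.** **1. Reproduce the plan's own count.** Safety laboratory visits in Table I: V1, V2, V4, V5, V8, V10, V11, which is 7. The list in 15.4.2 gives the same seven, and 13.1 states seven. In days: screening, 1, 8, 15, 43, 85, 210.

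**2. Classify each stated change.** A change is computable only if both ends have a scheduled laboratory draw.

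| Stated change | As written (before dose 2 = Day 29) | Lenient (before dose 2 = Day 15) |
|---|---|---|
| Baseline to before dose 2 | no | yes |
| Baseline to Day 57 | no | no |
| Before dose 2 to Day 57 | no | no |
| Baseline to Day 85 | yes | yes |
| **Empty** | **3 of 4** | **2 of 4** |

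The count of four treats the compound Day 57 phrase as two changes, which is the plain reading. Counted as one, the result is 2 of 3 as written and 1 of 3 on the lenient reading. The lenient reading carries the last-observation rule of 15.1.1 forward to dose 2. The documents do not say this, and the sentence itself names Day 29. On every reading, the number of computable stated changes that end after Day 29 and before Day 85 is 0.

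**3. Can visit windows supply a value?** Widest windows, from 12.2:

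- V5 (15 ± 2): Days 13–17
- V6 (29 ± 3): Days 26–32
- V8 (V6 plus 12 to 16 days): Days 38–48
- V9 (57 ± 2): Days 55–59
- V10 (85 ± 2): Days 83–87

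The nearest draw to V6 is 26 − 17 = 9 days earlier or 12 days later. The nearest to V9 is 55 − 48 = 7 days earlier or 83 − 59 = 24 days later. Section 12.4 gives ± 2 days for V6, so V6 is Days 27–31 and V8 ends at 31 + 16 = 47. The earlier gaps then grow to 27 − 17 = 10 and 55 − 47 = 8 days. No laboratory draw can fall in either window.

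**4. Can another rule supply a value?** Unscheduled samples are excluded by 15.1.1, and imputation by 15.2. The last-observation rule can fill the start of a change (Day 15) but not a Day 57 end point.

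**5. Does blood volume show that nine draws were intended?** With seven: 7×20 + 2×40 + 7×9 = 140 + 80 + 63 = 283 mL. With nine: 140 + 80 + 81 = 301 mL. Section 13.1 says approximately 300 mL, and both fit. The volume does not decide the matter; the stated count of seven and Table I do.

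**6. Check a repair on the existing schedule.** Baseline to Day 15, baseline to Day 43, Day 15 to Day 43 and baseline to Day 85 all have draws at both ends, so 0 of 4 are empty. Day 15 to Day 43 spans nominally 28 days (range 38 − 17 = 21 to 48 − 13 = 35). Day 15 is nominally 14 days before dose 2 (26 − 17 = 9 to 32 − 13 = 19), and Day 43 is 12 to 16 days after it.

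**The case against.** The strongest reply is that this is a slip in one parenthesis. The values are collected, listed by visit and listed again when out of range (15.4.2), and recorded as adverse events when clinically significant (14.6). They also fall under the general statement in 15.1.1 that "data recorded during the study will be summarized using descriptive statistics by treatment (placebo or vaccine) and dose group, unless otherwise specified". Section 15.4.2 names no test of laboratory changes, and no rule in 12.5 to 12.7 uses them. Section 15 defers detail to an SAP. All of this stands and keeps the severity low. It does not make the derivation possible: the protocol fixes the time points itself, so the SAP has to correct them, not merely elaborate them.

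Section 12.3 allows safety time points to change and unscheduled assessments to be made. That is a permission, not a scheduled draw at Day 29 or Day 57.

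A reader might infer four stronger things that the documents do not support.

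- **No laboratory safety data exist between dose 2 and Day 85.** They do: Day 43 bloods are drawn and listed. Only a specified, computable change is missing.
- **Laboratory baseline is undefined.** Section 15.1.1 uses the last observation before dosing. Urinalysis changes start from screening because no urinalysis is scheduled at Visit 2, which agrees with that rule. What is unstated is only whether the Visit 2 safety blood precedes the injection.
- **Replacement time points will be picked after the data are seen.** The SAP could fix them first; nothing says that it will not.
- **Nine draws were intended.** The volume figure fits seven as well as nine.

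**Conclusion.** The change rule in 15.4.2 is wrong as written: it names two visits at which 12.2, 13.1, Table I and its own visit list schedule no haematology or biochemistry. Three of four stated changes are empty (2 of 3 with the compound phrase counted once). Two of four (1 of 3) are empty if Day 15 is accepted as the value before dose 2. No reading leaves a computable stated change that isolates dose 2 or ends between dose 2 and Day 85.

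The grade is minor to should-fix. The data needed for sensible changes are already collected, and nothing in the conduct of the trial depends on these derivations. The conclusion assumes that the schedule, on which four places agree, is the intended one and that the change sentence is the outlier. If it is the other way round, the mismatch is the same but the repair differs.

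**What to change.** Reconcile 15.4.2 with 12.2, 13.1 and Table I before unblinding, in the protocol or in the SAP.

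If the existing schedule stands, define the laboratory changes as:

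- baseline to Day 15 (after dose 1);
- baseline to Day 43, and Day 15 to Day 43 (after dose 2);
- baseline to Day 85.

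Baseline to Day 8 is optional. State that the Day 15 value is nominally 14 days before dose 2 and may still reflect dose 1, so Day 15 to Day 43 is not a clean second-dose effect.

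Keep the 15.1.1 rule for baseline and add one sentence to the Visit 2 entry in 12.2 saying whether the safety blood is taken before dosing. If it is not, baseline under that rule is the screening value, 1 to 28 days before Day 1. The change to nominal Day 85 would then span 84 + 1 = 85 to 84 + 28 = 112 days instead of 84.

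Cost: a text correction in 15.4.2 and one sentence in 12.2, carried into the SAP, with no new samples or visits.

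If draws at Days 29 and 57 were intended, 12.2, 13.1, 15.4.2 and Table I must all say so. That means nine laboratory samples instead of seven, and an itemised volume of 301 mL instead of 283 mL per subject.
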